5.1.3 Concomitant medication date imputation

Table 3 below should be used to determine whether medications are concomitant or not. If a medication is considered concomitant it should be reported in each treatment period in which it is administered. The rules below for determining if a medication is concomitant should be applied to determine if the medication is concomitant within a particular period by using the start and end dates of the treatment period rather than overall start and end dates of study medication. The phases are defined in [Section 2.1.1](#). In the event that the medication could have potentially started in either phase then it should be considered concomitant in both.

Table 4: Concomitant medication date imputation

START DATE	STOP DATE	ACTION
Known	Known	
If stop date < study med start date, assign as prior
 
If stop date \geq study med start date and start date \leq study med end date, assign as concomitant
 
If stop date \geq study med start date and start date $>$ study med end date, assign as post study

	Partial	
Impute stop date as latest possible date (i.e. last day of month if day unknown or 31st December if day and month are unknown), then:
 
If stop date < study med start date, assign as prior
 
If stop date \geq study med start date and start date \leq study med end date, assign as concomitant
 
If stop date \geq study med start date and start date $>$ study med end date, assign as post treatment

	Missing	
If stop date is missing could never be assumed a prior medication
 
If start date \leq study med end date, assign as concomitant
 
If start date $>$ study med end date, assign as post treatment

START DATE	STOP DATE	ACTION
Partial	Known	
Impute start date as earliest possible date (i.e. first day of month if day unknown or 1st January if day and month are unknown), then:
 
If stop date < study med start date, assign as prior
 
If stop date \geq study med start date and start date \leq study med end date, assign as concomitant
 
If stop date \geq study med start date and start date $>$ study med end date, assign as post treatment

	Partial	
Impute start date as earliest possible date (i.e. first day of month if day unknown or 1st January if day and month are unknown) and impute stop date as latest possible date (i.e. last day of month if day unknown or 31st December if day and month are unknown), then:
 
If stop date < study med start date, assign as prior
 
If stop date \geq study med start date and start date \leq study med end date, assign as concomitant
 
If stop date \geq study med start date and start date $>$ study med end date, assign as post treatment

	Missing	
Impute start date as earliest possible date (i.e. first day of month if day unknown or 1st January if day and month are unknown), then:
 
If stop date is missing could never be assumed a prior medication
 
If start date \leq study med end date, assign as concomitant
 
If start date $>$ study med end date, assign as post treatment

Missing	Known	
If stop date < study med start date, assign as prior
 
If stop date \geq study med start date, assign as concomitant
 
Cannot be assigned as 'post treatment'

START DATE	STOP DATE	ACTION
	Partial	Impute stop date as latest possible date (i.e. last day of month if day unknown or 31st December if day and month are unknown), then: If stop date < study med start date, assign as prior If stop date >= study med start date, assign as concomitant Cannot be assigned as 'post treatment'
	Missing	Assign as concomitant

5.1.3.1 Prior therapies date imputation

Refer to Section 5.1.3 above.

5.1.3.2 Post therapies date imputation

Refer to Section 5.1.3 above.

5.1.3.3 Other imputations

Not applicable.

5.2 AEs coding/grading

The verbatim term recorded on CRF will be identified as adverse event and will be coded by primary system organ class and preferred term using Medical Dictionary for Regulatory Activities (MedDRA) version 21.0 and above.

5.3 Laboratory parameters derivations

Not applicable.

5.4 Assessment windows, baseline and post baseline definitions, missing data handling

During the period of the study from Screening to Follow-up Week 64 (F64), the assessments must be performed as indicated in Table 6.1 of the protocol.

Patients should be seen for all visits on the designated day or as closely as possible to the original planned visit schedule.

- For visits scheduled through Week 4, the study treatment should not be administered less than 4 days from the previous administration.
- For visits scheduled after Week 4, the study treatment should not be administered less than 14 days from the previous administration.

Assessment windows

No assessment windows have been defined for this study. Visit windows are described below.

Visits windows

Visit-windows will be used for the data that is summarized by visit; they are based on the study evaluation schedule and comprise a set of days around the nominal visit day. For any assessment, there are the protocol defined scheduled visits around which visit windows were created to cover the complete range of days within the study. The visit windows are shown in Table 4. In this table, the days are counted since the first dose of study treatment (study days) for safety and efficacy assessments. These visit windows apply to measurements taken at every visit. For assessments collected less often different visit windows will be applied as detailed below.

When visit windows are used, all visits will be re-aligned, i.e., they will be mapped into one of the visit windows. E.g., if the *Week 4* visit of a subject is delayed and occurs on Day 46 instead of on Day 29, say, it will be re-aligned to visit window *Week 8*. In the case of major deviations from the visit schedule, or due to unscheduled visits, several assessments of a subject may fall in a particular visit window (either scheduled or unscheduled). Statistical approaches to handle multiple assessments in a given visit window are specified below.

Of note, subjects are allowed to have gaps in visits.

Table 5-1: Assessment windows for scheduled visits

Analysis Visit	Week	Scheduled Day	Visit Window
Baseline	BSL	1	-28 days to Day 1*
Week 1	1	8	Day 2-11
Week 2	2	15	Day 12-18
Week 3	3	22	Day 19-25
Week 4	4	29	Day 26-43
Week 8	8	57	Day 44-71
Week 12	12	85	Day 72-99
Week 16	16	113	Day 100-127
Week 20	20	141	Day 128-155
Week 24	24	169	Day 156-211
Week 36	36	253	Day 212-309
Week 52	52	365	Day 310-379
Week 56	56	393	Day 380-421
Week 64	64	449	Day 422-463

* Baseline measurement before the first drug administration for safety assessments and before the randomization for efficacy assessments. The days are counted since the first dose of study treatment for safety assessments, and the days are counted since the date of randomization for efficacy assessments.

For parameters which are not collected at every visit, visit windows defined in Table 4 will be combined. For example, if a parameter is measured at Week 12 and Week 24 only, Week 12 visit window will extend from Day 2 to Day 99 (combining Week 1 to Week 12 visit windows), Week 24 will extend from Day 89 to Day 211 (combining Week 13 to Week 24). If more than one assessment falls into the interval, the rules defined below are applied.

Assessments from one treatment period will not be considered for another treatment period. For example, if a Week 13 (scheduled visit) measurement falls into the Week 12 visit window, this measurement would not be analyzed as treatment period 1 value.

Of note, for subjects who discontinue in treatment period 1, i.e. not moving into treatment period 2, efficacy measurements taken in follow-up period would still be considered for the treatment period 1.

The analysis visit will be used for listing of visit and treatment period for safety data. If a visit falls after the last visit window (after Day 463) it is not assigned an analysis visit and will be listed under label “After Week 64”.

The administration of study drug at Week 28, 32, 40, 44, and 48 is not in relation to a study visit. For exposure data, a specific assessment window for those weeks is used in order to account for the home administrations at those weeks.

Table 5-2: Drug administration windows for scheduled visits of Exposure Data

Analysis Visit	Week	Scheduled Day	Visit Window
Baseline	BSL	1	-28 days to Day 1*
Week 1	1	8	Day 2-11
Week 2	2	15	Day 12-18
Week 3	3	22	Day 19-25
Week 4	4	29	Day 26-43
Week 8	8	57	Day 44-71
Week 12	12	85	Day 72-99
Week 16	16	113	Day 100-127
Week 20	20	141	Day 128-155
Week 24	24	169	Day 156-183
Week 28	28	197	Day 184-211
Week 32	32	225	Day 212-239
Week 36	36	253	Day 240-267
Week 40	40	281	Day 268-295
Week 44	44	309	Day 296-323
Week 48	48	337	Day 324-351
Week 52	52	365	>= 352 Days

Multiple assessments within visit windows

When there are *multiple assessments* in a particular visit window, the following rules are applied to select one value “representing” the subject in summary statistics in a visit window (See Table 5).

For baseline assessment definition see [Section 2.1.1](#). For post-baseline visit windows the following applies (unless otherwise specified):

- for *quantitative variables*, the *closest* to the actual visit is chosen (if two assessments have the same distance, then the earlier one will be chosen)
- for *qualitative variables*, the *worst* record is selected. It is noted that in the analyses performed, *worst* case is always well defined (e.g., for urine protein values “+” and “++”, the worst case is defined as “++”)
- in case qualitative variables are based on quantitative variables, e.g. PASI 75 response, the visit will be assigned to the quantitative variable, and this visit will be used for the derived qualitative variable

Table 6: Rules for selecting values for analysis

Timing of measurement	Type of data	Rule
Baseline	All data	See Section 2.1.1
Post-baseline efficacy	Continuous data	The measurement closest to the target day will be used. In the event two measurements are taken equally apart (e.g., 1 day before target date and 1 day after), the earlier one will be used
Post-baseline efficacy	Categorical data	The most extreme (the worst) measurement in the window will be used. For example, among 'a little better' and 'moderately better' values 'a little better' value will be selected.
Post-baseline safety	Continuous data	The (non-missing) measurement closest to the target day will be used. In the event two measurements are taken equally apart (e.g., 1 day before target date and 1 day after), the earlier one will be used. If two measurements are taken on the same day then select the first one (using the time). If two measurements are taken on the same date/time then use the first visit number (assuming this is the planned visit).
Post-baseline safety	Categorical data	The most extreme (the worst) measurement in the window will be used. For example, among 'a little better' and 'moderately better' values 'a little better' value will be selected

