A blinded sample size estimation (SSR) will be performed when the first 60 patients have completed the Week 12 visit as described in Section 2.15.

Treatment Period 3 – extension period (Week 24 to Week 52)

Treatment Period 3 is an extension period to allow responder patients (if they wish and as per clinician's judgment) the possibility to continue open-label secukinumab treatment up to Week 52.

At Week 24, open-label secukinumab will continue to be assigned to patients in Group 1 and Group 2 at the same dose every 4 weeks until Week 52 at either the study site (i.e. Week 24, 36 and 52) or at home (Week 28, 32, 40, 44, 48).

At Week 24, patients who do not reach at least a 20% improvement in tender joint count (TJC) and swollen joint count (SJC) with secukinumab (150 mg or 300 mg) will be withdrawn from the study.

The Week 24 analysis will be performed after all patients complete the Week 24 visit (see Section 2.15).

The final analysis will be performed after the last patient has completed the Week 64/End of Study visit or early withdrawal visit (in case of early withdrawal of last patient from the study). After the final database lock and analyses have been completed, site personnel

(including the Ultrasonography Investigator and Clinical Investigator) will be unblinded to the original randomized treatment (sequence) assignment at randomization.

A follow-up visit is to be done 12 weeks after last study treatment administration for all patients, regardless of whether they complete the entire study as planned or discontinue prematurely. All AEs that occur during this post-treatment follow-up period will be included in the evaluation of treatment-emergent AEs.

The study population will consist of male and female patients aged ≥ 18 years with PsA as per the classification criteria for PsA (CASPAR) and with active PsA for at least 6 months and must have active disease as assessed by ≥ 3 tender joint count (TJC) out of 78 and ≥ 3 swollen joint count (SJC) out of 76 at Baseline and with an IR to non-biologic DMARDs and at least one clinical enthesitis at Screening and Baseline. Patients can be re-screened only once and 'no' re-screening study related procedures should be performed prior to written re-consent by the patient. Mis-randomized patients cannot be re-screened. The goal is to randomize 164 patients in total (82 patients per arm) at approximately 50 centers worldwide.

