2.1.1 General definitions

Treatment periods

Period 1 = from first dose up to but not including Week 12 dose.

Period 2 = Week 12 dose up to but not including Week 24 dose.

Extension = Week 24 dose until Week 52.

Follow-up = After Week 52 until Week 64

Study Day 1 and other study days

The first day of administration of randomized study treatment (first dose) is defined as *Study Day 1 or Day 1*.

All other study days will be labeled relative to Day 1. For event dates on or after Day 1, study day for a particular event date is calculated as [Date of event] – [Date of first dose]+1, i.e., Day 2, Day 3, etc., will be one day, two days, etc., after Day 1, respectively. For the dates before Day 1, study day for an event date is calculated as [Date of event] – [Date of first dose], i.e., Day -1, Day -2, etc., will be one day, two days, etc., before Day 1, respectively. Duration of an event will be calculated as (Event end date – Event start date + 1).

The descriptor “Day 0” will not be used.

Screening, baseline and post-baseline definitions

Screening refers to any procedures (e.g., checking inclusion and exclusion criteria) performed prior to the date of first dose of study treatment. Per protocol, subject informed consent must be obtained prior to performing any study related activity. The date of signing informed consent is the start date of screening period. Any assessment

obtained during the screening period will be labeled screening assessment. Assessments made on Day 1 may occur before or after the randomization or the first dose.

For efficacy analyses, baseline is the last assessment (including unscheduled visits) obtained before the first dose of study treatment . All assessments obtained after the first dose of study treatment are considered as post-baseline unless otherwise specified.

For safety analyses, baseline is the last assessment (including unscheduled visits) obtained before the first dose of study treatment. All assessments obtained after the first dose of study treatment are considered as post-baseline unless otherwise specified.

Of note, re-randomization will not be used for baseline definition and only one baseline value will be defined referring to the first randomization.

Day of last dose of randomized study treatment

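### Follow-up is defined only as after Week 52, so the visit 12 weeks after last dose of patients stopping in Period 2 or 3 is usually mapped to the Week 24, 36 or 52 window

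*SAP*

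**What the plan says.** Section 1.1 ties the follow-up visit to the last dose: "A follow-up visit is to be done 12 weeks after last study treatment administration for all patients", whether or not they complete the study. It treats that time as post-treatment: "All AEs that occur during this post-treatment follow-up period will be included in the evaluation of treatment-emergent AEs".

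Section 2.1.1 defines the periods differently. The second open-label stage is set by its doses: "Period 2 = Week 12 dose up to but not including Week 24 dose". The stage after it also starts with a dose but ends on a calendar week: "Extension = Week 24 dose until Week 52". Time off treatment is set by calendar week alone: "Follow-up = After Week 52 until Week 64". None of these definitions refers to the patient's own last dose, and none says how a period ends for a patient who stops early.

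Section 5.4 counts days from first dose and states that "When visit windows are used, all visits will be re-aligned, i.e., they will be mapped into one of the visit windows". Table 5-1 gives Week 24 Days 156–211, Week 36 Days 212–309, Week 52 Days 310–379, Week 56 Days 380–421 and Week 64 Days 422–463. For safety data, "The analysis visit will be used for listing of visit and treatment period for safety data".

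Two other rules in section 5.4 bear on the point. Values from one treatment period are not to be used for another. For patients who stop in Period 1, efficacy values from follow-up still count towards Period 1. No matching rule exists for Period 2 or 3.

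**The concern.** Section 1.1 runs follow-up on a clock that starts at the last dose. Sections 2.1.1 and 5.4 run it on a clock that starts at the first dose. The two agree for a patient who completes treatment at Week 52. For a patient who stops earlier, the follow-up visit has no label of its own and takes whichever scheduled week its study day falls in.

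The outputs at stake are the by-visit laboratory summaries (section 2.9.5), the by-visit vital-sign summaries (section 2.9.7.2), observed-case efficacy after Week 12 (sections 2.5.3 and 2.6.3) and the by-visit PK summary (section 2.10). In each, a value taken 12 weeks after the last dose could sit under the same heading as values from patients still being dosed.

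**Working it through.** **Inputs.** Dosing from Week 12 is at Weeks 12, 16 and 20 (Period 2), then Weeks 24, 28, 32, 36, 40, 44, 48 and 52 (Period 3), from section 1.1. Follow-up is 12 weeks = 84 days after last dose (section 1.1). Windows are from Table 5-1. I take first dose and randomization to be on the same day, and the parameter to be collected at every visit in Table 5-1. If it is not, section 5.4 merges windows and the label may shift.

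**Formulas.** Dose day = 7 × week + 1. Follow-up day = dose day + 84.

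**Check against the plan's own figures.** Week 52 dose: 7 × 52 + 1 = 365, and 365 + 84 = 449, the scheduled day of Week 64 in Table 5-1. The SAP's example of Day 46 falling in Week 8 (Days 44–71) also reproduces.

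**Early stops.**

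| Last dose | Dose day | Follow-up day | Window |
|---|---|---|---|
| Week 12 | 85 | 169 | Week 24 (target day) |
| Week 16 | 113 | 197 | Week 24 |
| Week 20 | 141 | 225 | Week 36 |
| Week 24 | 169 | 253 | Week 36 (target day) |
| Week 28 | 197 | 281 | Week 36 |
| Week 32 | 225 | 309 | Week 36 (last day) |
| Week 36 | 253 | 337 | Week 52 |
| Week 40 | 281 | 365 | Week 52 (target day) |
| Week 44 | 309 | 393 | Week 56 |
| Week 48 | 337 | 421 | Week 56 |

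By study day alone, 8 of 10 positions fall in the Week 24, 36 or 52 window. Moving the visit by up to 7 days does not change that count. Last doses at Weeks 44 and 48 map to Week 56, after Week 52, and are not affected.

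**Does the cross-period rule remove these visits?**

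- *Last dose Week 12 or 16.* The patient never has the Week 24 dose, so by section 2.1.1 never leaves Period 2. A value in the Week 24 window is not excluded.
- *Last dose Week 24, 28, 32, 36 or 40.* The Extension runs until Week 52, so the visit counts as Extension data. It is not excluded.
- *Last dose Week 20.* The Extension begins with the Week 24 dose, which this patient does not have. The Day 225 value is then arguably a Period 2 value in a later period's window, and the rule may exclude it for efficacy. For safety data the period is read from the analysis visit, which is Week 36, so the rule gives no independent check.

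That leaves 2 + 5 = 7 of 10 positions without the Week 20 case, and 8 of 10 with it.

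**Do the other rules help?** Section 2.9 limits safety tables to visits planned in the protocol, but by section 1.1 the follow-up visit is itself planned. Where a window holds several values, the closest to target is used for continuous data and the worst for categorical data. A follow-up value on a target day (last dose Week 12, 24 or 40) cannot be displaced by a closer one. Table 5-1 has no visit between Weeks 24 and 36, so a follow-up visit there may be the patient's only value in the window.

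**The case against.** Five arguments stand against the point.

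1. Section 5.4 labels visits by time since first dose and does not call them on-treatment. Section 2.1 presents later data by treatment sequence, and open-label data are observed case. Summarising everyone seen around Week 36 is a defensible choice. This stands in part, but the SAP never states that choice, and section 1.1 calls the same visit post-treatment.
2. Exposure (section 2.4.1) and treatment-emergent AEs (section 2.9.1) run to last dose + 84 days, so the visit lies at the edge of time the SAP counts as exposed. This stands for AE attribution. It does not make a post-treatment visit a scheduled Week 36 visit.
3. The Period 1 efficacy rule reads like an exception, which might imply that other early follow-up efficacy values are left out. The SAP does not say so, and the rule does not cover safety data.
4. The sentence on safety periods speaks of listings. That is fair, but the by-visit tables use the same windows and no other source for the period is given.
5. The assessments made at the follow-up visit are set by the protocol schedule, which is not shown. The efficacy and PK consequences are therefore conditional.

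A reader might also infer that the patients withdrawn at Week 24 (those without the required "improvement in tender joint count (TJC) and swollen joint count (SJC) with secukinumab (150 mg or 300 mg) will be withdrawn from the study") are the largest affected group and reappear as Week 36 efficacy values. The text does not support this. If their last dose was at Week 20 they never enter the Extension as defined, so the cross-period rule may keep their efficacy value out, and the SAP gives no figure for the size of that group.

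**Conclusion.** The point holds as a labelling gap. Following sections 2.1.1 and 5.4 as written, the follow-up visit of a Period 2 or 3 stopper enters the Week 24, 36 or 52 window for 7 of 10 scheduled last-dose positions. The count is 8 of 10 if Week 20 is included, which is the more natural reading for safety data and an open question for efficacy.

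These are counts of dosing positions, not of patients. The only drop-out figure in the SAP is 5% before Week 12 (section 3.1), so neither the number of affected patients nor the shift in any mean can be derived.

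The consequence is confined to post-Week 12 summaries: laboratory and vital signs, and observed-case efficacy or PK where collected at that visit. The primary and key secondary analyses at Week 12 are untouched. The non-responder-imputation analyses of ACR and PASI to Week 52 are not affected either. It should be corrected, but it does not threaten the trial's main conclusions.

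**What to change.** In section 2.1.1, define Follow-up per patient as assessments at the post-treatment follow-up visit, and reconcile this with sections 1.1 and 5.4. In section 5.4, give that visit its own analysis-visit label, for example *Follow-up, 12 weeks after last dose*. For patients stopping in Period 2 or 3, keep it out of the Week 16 to Week 52 windows in by-visit summaries. Leave unchanged the Period 1 efficacy rule and the last dose + 84 days rules for treatment-emergent AEs and exposure.

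The cost is SAP wording and one programming flag, presumably from the recorded visit label. No new data are needed. The downside is slightly fewer observed-case values at those visits. The Week 36 and Week 52 summaries would then describe patients still on treatment and should be labelled so.

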2.6.3 Handling of missing values/discontinuations

Missing data for the ACR 20 response and other binary efficacy variables (e.g. ACR 50, ACR 70, [REDACTED] PASI 75, PASI 90, PASI 100) for data up to 12 weeks (Week 12) will be handled as follows:

- Patients who drop out of the trial for any reason will be considered non-responders from the time they drop out through to Week 12.
- Patients who do not have the required data to compute ACR response (i.e. TJC and SJC and at least 3 of the 5 ACR core set variables) at the specific post-baseline time points will be classified as clinical non-responders.

The following continuous variables: ACR components, HAQ-DI[®] score, PDUS score and its components will be analyzed using a MMRM, which is valid under the MAR assumption. For analyses of these parameters, if all post-baseline values are missing then these missing values will not be imputed and the patient will be removed from the analysis of the corresponding variable, i.e. it may be that the number of patients providing data to an analysis is smaller than the number of patients in the FAS.

Data collected during the open label period (after Week 12) will generally be presented as 'observed case'; i.e. all available data for each time point will be included in the analyses.

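### A late Week 12 assessment taken after Day 99 but before the first open-label dose has no valid analysis visit, so an observed ACR responder can be scored a non-responder

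*SAP*

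**What the plan says.** Four rules of the SAP meet here.

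- **Treatment periods (Section 2.1.1).** "Period 1 = from first dose up to but not including Week 12 dose", and "Period 2 = Week 12 dose up to but not including Week 24 dose". The boundary is a dosing event, not a study day.
- **Visit windows (Section 5.4, Table 5-1).** With windows, "all visits will be re-aligned, i.e., they will be mapped into one of the visit windows". Week 12 has target Day 85 and window Day 72-99; Week 16 has Day 100-127. The SAP's own example moves a Week 4 visit held on Day 46 into Week 8, so study day overrides the nominal label.
- **Period rule (Section 5.4).** "Assessments from one treatment period will not be considered for another treatment period". The only example is a Week 13 measurement that falls in the Week 12 window and is kept out of Period 1.
- **Missing ACR data (Section 2.6.3).** Up to Week 12, patients without the required components "at the specific post-baseline time points will be classified as clinical non-responders".

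For responses derived from quantitative measures, Section 5.4 adds that "the visit will be assigned to the quantitative variable, and this visit will be used for the derived qualitative variable". Its one exception concerns patients who stop in Period 1: their "efficacy measurements taken in follow-up period would still be considered for the treatment period 1".

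**The concern.** When a visit is late within one treatment period, re-alignment moves its value to the next window and the value is still used. At Week 12 the next window belongs to a different period. A value obtained before the first open-label dose is Period 1 data under Section 2.1.1, but from Day 100 its study day places it in a Period 2 window. No rule returns it to Week 12.

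H1 to H4 in Section 2.6.2 are all tested on Week 12 results. For GLOESS (H1) and SPARCC (H4) the consequence is one missing visit. For ACR 20 (H2) and ACR 50 (H3) it is an imposed failure in a patient whose response may have been measured under blinded, randomized treatment. If the programmer instead lets re-alignment prevail, a placebo patient's placebo-phase value appears as a Week 16 result, a visit at which everyone is on open-label secukinumab.

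**Working it through.** **1. The SAP's own figure.** Section 3.1 states more than 90% power for ACR 20 and ACR 50. Inputs from that section: 82 patients per arm; placebo 29.6% and 10.7%; secukinumab 63.5% and 33.3%. Section 2.6.2 gives a 1-sided 5% level. With a pooled variance under the null hypothesis,

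power = Φ[(d − 1.645·SE0)/SE1], where SE0 = √(2·p̄(1−p̄)/82) and SE1 = √((p1(1−p1)+p2(1−p2))/82).

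- ACR 20: d = 0.339, p̄ = 0.4655, SE0 = 0.0779, SE1 = 0.0733. Power = 99.8%.
- ACR 50: d = 0.226, p̄ = 0.220, SE0 = 0.0647, SE1 = 0.0622. Power = 97.3%.

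The stated figure is reproduced.

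**2. Following the rules for one patient.** The patient attends Week 12 on Day 100, is assessed, then receives the first open-label dose.

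- Lateness: 100 − 85 = 15 days.
- Period: the assessment precedes the Week 12 dose, so it is Period 1.
- Window: Day 99 would be Week 12; Day 100 is Week 16.
- Period rule: a Period 1 value may not serve Period 2, so it is barred from Week 16.
- Combined windows do not help. In the SAP's example the "Week 12 visit window will extend from Day 2 to Day 99", so the window grows backwards only. For a measure not collected at Week 16, Day 100 falls in a later open-label window instead.
- The exception for patients who stop in Period 1 does not apply, because this patient continues.
- If Day 72-99 holds no other assessment, there is no Week 12 value. ACR 20 and ACR 50 are set to non-response, and GLOESS and SPARCC are missing at Week 12.

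The boundary itself also needs settling. The text of Section 5.4 counts days from first dose for both safety and efficacy, but the footnote to Table 5-1 counts efficacy days from randomization.

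**3. Size.** The share f of patients affected is not in the SAP. If it is equal in both arms and these patients respond at the planned rates, each response rate is multiplied by (1 − f), and so is the difference.

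| f (assumed) | ACR 20 difference, points | 1-sided power | ACR 50 difference, points | 1-sided power |
|---|---|---|---|---|
| 0 | 33.9 | 99.8% | 22.6 | 97.3% |
| 2% | 33.2 | 99.7% | 22.1 | 97.0% |
| 5% | 32.2 | 99.6% | 21.5 | 96.4% |
| 10% | 30.5 | 99.3% | 20.3 | 95.3% |
| 15% | 28.8 | 98.7% | 19.2 | 94.0% |

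At 1%, the ACR 20 difference is 33.9 × 0.99 = 33.6. A range of 1-5% of 164 is 1.6 to 8.2 patients. At 5%, the ACR 20 responders recoded are 82 × 0.635 × 0.05 = 2.6 on secukinumab and 82 × 0.296 × 0.05 = 1.2 on placebo. For ACR 50 they are 1.4 and 0.4.

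**4. Uneven lateness, as a bound only.** With 10% affected on secukinumab alone, the ACR 20 difference is 0.635 × 0.9 − 0.296 = 27.6 points. With 10% affected on placebo alone, it is 0.635 − 0.296 × 0.9 = 36.9 points.

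**The case against.** The strongest reply is that this is what any finite window does. Section 5.4 says openly that late visits move and that gaps are allowed, Week 12 already has about two weeks on either side, and scoring absent ACR data as non-response is pre-specified. That would be sufficient if the value moved to a usable window, as in the Week 4 example. Here the next window lies in another treatment period, so the value is either barred or mislabelled.

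A second reply is that no sentence says the value is discarded. The period rule could be read as keeping it in Period 1. That is fair: a reader might infer that the SAP orders the data to be thrown away, and it does not. But on each of these readings, no rule makes it the Week 12 value.

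Several limits stand:

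- The frequency is unknown. Section 5.4 asks for visits as close to schedule as possible.
- If the whole schedule slipped, a delayed Week 8 visit may fall in Day 72-99 and stand in for Week 12. The patient is then neither missing nor automatically a non-responder.
- For GLOESS and SPARCC the patient's earlier visits remain in the mixed model. Absence caused by scheduling is a plausible case of missing at random, so the cost is a little precision.
- Equal lateness attenuates the ACR differences, which is conservative for superiority.

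**Conclusion.** The point holds as a gap between the period definition and the day-based windows. It affects patients who continue, whose pre-dose Week 12 assessment falls on Day 100 or later, and who have nothing else in Day 72-99. For them the rules leave Week 12 empty and score a measured ACR response as failure.

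At an assumed 1-5% in both arms, the ACR 20 difference falls from 33.9 to 33.6-32.2 points. Power stays above the stated 90%, and does so even at 15% (98.7% for ACR 20, 94.0% for ACR 50). These figures assume equal lateness and planned response rates among late patients.

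A reader might go further and infer that the randomized comparison is biased in a known direction, or that H1 is in jeopardy. The SAP does not support either. It gives no reason for lateness to differ by arm during blinded treatment, so the uneven scenarios are only bounds, and H1 loses at most one visit per affected patient. The case for acting is a correct, unambiguous derivation of the Week 12 endpoints and less bias in the ACR rates.

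**What to change.** Add to Section 5.4, for efficacy: *For patients who enter Period 2, an assessment made before the first Period 2 dose is never assigned to Week 16 or later. If there is no assessment in Day 72-99, the pre-dose assessment closest to Day 85, up to a stated cap, is used as Week 12.* Day 127, the end of the Week 16 window, is one possible cap. Without a cap, a very late assessment would still count as Week 12.

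For patients who do not enter Period 2, keep the existing rule on follow-up efficacy measurements and state the same day cap for it. A separate Day 99 limit for them would conflict with that rule. State the reference day for efficacy windows once, so that Day 99 and Day 100 have one meaning.

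The cost is two sentences, a cap, and a change to the visit-derivation program. The rule uses dates only, so it can be fixed without sight of outcomes. The downside is that a few Week 12 values will come from after Day 99; a sensitivity analysis with the strict Day 72-99 window shows their effect.
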